All of Ontario's 26 regional renal programs and their associated multidisciplinary kidney care clinics (MCKC) will be included. These programs provide care for all chronic dialysis patients. Each CKD program also provides a MCKC for pre-dialysis patients. We will be restricting to pre-dialysis patients with an eGFR <15mL/min/1.73m² (defined as two outpatient eGFR measurements meeting this criterion within the last year) OR a 2-year KFRE ≥25% (defined as two KFRE measurements meeting this criterion within the last year).

Considering your inclusion criteria listed above, what is the basis to exclude a potential participant?

Not applicable, we will be including all Ontario renal programs.

If using patients, describe the usual standard of care at the study site(s) for this population

Currently, there is no standard of care to improve access to kidney transplantation at the Ontario renal programs. Renal programs may provide education to their patients on treatment modalities (i.e., hemodialysis, peritoneal dialysis, transplant). The renal programs also currently provide program-level performance reports on different metrics (e.g., transplant rates); however, these are not based on best practices in audit and feedback.

Describe the study procedures and any study specific testing that will be done, outside of standard care.

The multicomponent kidney transplant quality improvement program will be at the level of the renal program, rather than the individual patient. As a result, all patients within a program will receive similar care.

How many participants over the age of 18 will be included at all study locations?

26 renal programs and their associated multidisciplinary kidney care clinics.

How many participants under the age of 18 will be included at all study locations?

No renal programs treat children exclusively; however, there could be some children transitioning to adult care.

Describe the method(s) of data analysis.

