		
5. Pre-emptive living donor kidney transplants (restricted to patients who were not receiving dialysis when they entered the trial and not on dialysis at the time of transplant).
 
Description: Secondary outcome selected to understand living kidney donor transplant activity.
 
Time Frame: 4.17 Years
	
Other pre-specified outcomes	August 7, 2020	
Added: We will consider several other outcomes in an exploratory analysis. Other outcome measures, include:
 
 1. Rate of deceased donor kidney transplant Description: Rate of deceased donor kidney transplant censoring at death and receipt of a living donor kidney transplant. Time Frame: 4.1 Years 2. Average number of months from the date of dialysis initiation (i.e. trial entry) to the date of referral. Description: This outcome is assessed in patients receiving maintenance dialysis who were referred to a transplant centre. Time Frame: 4.1 Years 3. Rate of living kidney donor transplants Description: This outcome is assessed in patients waitlisted for a deceased donor kidney transplant and censored at death and receipt of a deceased donor kidney transplant. Time Frame: 4.1 Years 4. Proportion of pre-emptive transplants Description: This outcome is assessed in recipients of a living kidney donor transplant and restricted to patients who were not receiving dialysis when they entered the trial and not on dialysis at the time of transplant. Time Frame: 4.1 Years 5. Average number of months from the date of referral to a transplant centre to the date the first living donor candidate contacts the transplant centre for the intended recipient Description: This outcome is assessed in recipients of a living kidney donor transplant. 	All other outcomes provide additional important information about access to kidney transplant. Further details on these measures can be found in our published trial protocol.

Revision	Date of Revision	Details of Revision	Rationale

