	August 10, 2020 June 23, 2022 August 10, 2020	
effect to be the same for each state transition in our primary analysis. This approach will provide a single estimate of the relative rate (i.e., hazard ratio) of steps completed towards receiving a transplant among patients in CKD programs in the intervention group versus the usual-care group.
 
Changed from: We will censor at death or end of study.
 
Changed to: We will follow patients in our analysis until the end of study, death, receipt of a kidney transplant, or become ineligible for transplant, whichever comes first.
 
Added clarification: A patient's observation time will only stop on the trial end date (December 31, 2021), death, receipt of a kidney transplant, evidence of recovered kidney function, emigration, or on the date a recorded contraindication to transplant occurs (with the exception of age >75 years).
 
Added: A patient's follow-up time will begin on November 1, 2017 or on the earliest date when all eligibility criteria were met up until 3 months before the trial end date (3 months is the expected minimum time to complete early steps towards receiving a kidney transplant). Patients can only enter the analytic cohort once.
	
model, which are fully described in our published statistical analysis plan.
 
We have refined our censoring events to ensure our denominator is capturing the population of interest.
 
In our published protocol we indicated that we would stop following individuals when they become ineligible for transplant. We are also censoring at recovered kidney function as these individuals would not be actively taking steps towards a transplant. We will keep individuals in the trial analysis if they turn aged > 75 years during follow-up given they were 75 years when they entered the trial, and a small proportion of older individuals receive a kidney transplant. As described in our published statistical analysis plan, we will also be censoring at emigration from the province using updated methodology available using our administrative data sources.
 
We provide detail on the timeframe for entering the analytic cohort for analysis.

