	June 23, 2022	
other), immigration status, geography (average distance from the patient's place of residence to the transplant centre), income quintile (measured by neighbourhood-level median income), and measures of marginalization (i.e. residential instability, material deprivation, ethnic concentration, and dependency).
 
Changed to: We will not perform subgroup analyses of the intervention effect by race (white vs. other) or immigration status.
 
Added: In addition to the subgroup analyses described in our published protocol, we will also conduct subgroup analyses based on how the patient entered the trial (whether patients were approaching the need for dialysis or receiving maintenance dialysis as well as if patients entered on November 1, 2017 or during the accrual period).
 
Added Clarification: As specified in our protocol, the primary analysis for this trial will not account for pandemic-related changes in transplant activity. However, we will conduct an additional analysis in which patients' follow-up times will be truncated on the date transplant activity was first suspended in Ontario. We are also conducting a concurrent process evaluation using surveys and interviews to understand how the intervention was delivered in each CKD program, and we will ask respondents how the pandemic affected these activities.
	
After consultation with our project partners, we will not perform subgroup analyses by race and immigration status. We do not have access to self-reported race which is considered the gold standard for determining individuals' race and ethnicity. Ethnicity information in the Ontario Renal Reporting System was collected by data leads in each CKD program at the time of patient registration, based on charting by clinical staff who could ask patients to self-identify ethnicity but who were not mandated to do so.
 
We updated our subgroup analyses by including an analysis based on how the patient entered the trial. This was always an intended analysis but was not explicit in the published protocol. This information is detailed in our published statistical analysis plan.
 
Given the challenges of delivering the intervention during the COVID-19 pandemic, we will perform a pre-specified analysis of our primary and secondary outcomes restricting the trial period and follow up from November 1st, 2017 to December 20th, 2019 with follow up to March 16th, 2020. March 16th, 2020 aligns with the suspension of transplant activity in Ontario. It is possible any beneficial effect of the intervention will be more pronounced in the pre-pandemic period.

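### Other outcome 2 treats dialysis initiation and trial entry as the same date, which is false for patients already on dialysis on November 1, 2017

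*Combined protocol and SAP*

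**What the plan says.** The outcome appears in the Table of Protocol Updates, row on other pre-specified outcomes, item 2, added August 7, 2020: "Average number of months from the date of dialysis initiation (i.e. trial entry) to the date of referral". Its population is given in the next line: "This outcome is assessed in patients receiving maintenance dialysis who were referred to a transplant centre".

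Trial entry is fixed in the row on analysis of trial outcomes: "A patient's follow-up time will begin on November 1, 2017 or on the earliest date when all eligibility criteria were met". Entry stays open until 3 months before the trial end date, and a patient can enter only once.

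Two kinds of patient are in scope. The inclusion criteria in the protocol say of the renal programs: "These programs provide care for all chronic dialysis patients". For kidney clinic patients they say: "We will be restricting to pre-dialysis patients with an eGFR <15mL/min/1.73m²", with a KFRE threshold as the alternative route. The row on additional exploratory analyses adds subgroups by "whether patients were approaching the need for dialysis or receiving maintenance dialysis", and by entry on November 1, 2017 versus entry during accrual.

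The June 23, 2022 clarifications to the other outcomes reword items 1 and 3 and change the time frame from 4.1 to 4.17 years. The definition of item 2 is left as it was, so the wording quoted here is current text.

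**The concern.** The definition names two start dates for one interval and says they are the same. Under the plan's own entry rule they are not the same for patients already on dialysis when the trial began. If the analyst takes trial entry as time zero, as the parenthesis instructs, the result is labelled months from dialysis initiation. For established dialysis patients it would in fact be months from November 1, 2017. A reader would take the reported average as the delay between starting dialysis and being referred, and for long-term dialysis patients that could be wrong by years.

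**Working it through.** **The plan's own figure.** The only number attached to this outcome is the time frame. November 1, 2017 to December 31, 2021 is 1,522 days counted inclusively, and 1,522 / 365.25 = 4.167 years. The stated 4.17 years reproduces and is not in dispute.

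**Do the two dates coincide?** Applying the entry rule to each route into the cohort:

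| Route | Trial entry | Same as dialysis initiation? |
|---|---|---|
| First eligible on the day dialysis starts, during accrual | Dialysis start | Yes |
| Already on dialysis on November 1, 2017 | November 1, 2017 | No, unless dialysis began that day |
| Entered from a kidney clinic, dialysis later | November 1, 2017, or the date the eGFR or KFRE criteria were met if later | No |

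The second route is within the outcome's stated population on any ordinary reading. The third is within it only if receiving maintenance dialysis is not judged at entry, and the text does not settle that.

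**Size for one patient.** For a patient already on dialysis at entry:

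months from dialysis start = months from entry + months on dialysis before entry.

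- Dialysis start November 2013, entry November 2017, referral November 2018: 12 from entry; 12 + 48 = 60 from dialysis start.
- Referral 12 months after entry, with 12, 36 or 60 months of earlier dialysis: 24, 48 or 72 from dialysis start, against 12 from entry in every case.

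Entry-based values also have a ceiling. From November 1, 2017 to December 31, 2021 is 1,521 days elapsed, and 1,521 / 365.25 × 12 = about 50 months. Dialysis-based values have no such ceiling.

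**Size for the average.** The documents give neither the share of patients already on dialysis nor their prior time on it, so both are assumptions here. Let *p* be that share, *v* their mean prior months on dialysis, and let everyone else enter at dialysis start. With referral 12 months after entry for all, the mean from dialysis start is 12 + *p* × *v*, against 12 from entry:

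| *p* | *v* = 12 | *v* = 36 | *v* = 60 |
|---|---|---|---|
| 25% | 15 | 21 | 27 |
| 50% | 18 | 30 | 42 |
| 75% | 21 | 39 | 57 |

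The table shows how far the label and the quantity could separate. It does not estimate what this trial would find.

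**The case against.** The strongest reply is that the parenthesis is itself a restriction: it could mean that only patients whose dialysis start was their entry event are counted. On that reading the dates agree and the measure is sound. The plan also refers readers to a published trial protocol for detail on these outcomes, and the answer may be there. This cannot be excluded, but the restriction is not written here. The authors do write such limits elsewhere: other outcome 4 is confined by dialysis status at trial entry, and one planned subgroup is defined by receiving dialysis at entry.

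Three further points stand and limit the concern.

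- A reader might infer that the outcome fails to measure time from dialysis start to referral altogether. The documents do not support that. It is right for patients who enter at dialysis start.
- A reader might infer that clinic patients referred before dialysis will contribute negative values. That holds only if those who start dialysis later are included and their actual dialysis date is time zero, which the text does not establish.
- A reader might infer that a difference between arms would reflect the mix of entry routes. The same rule applies to both arms, randomization was covariate-constrained, and the documents give no group shares. That effect cannot be sized and should not be asserted.

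**Conclusion.** The point holds in limited form. The stated equality between dialysis initiation and trial entry contradicts the entry rule for patients already on dialysis on November 1, 2017. It also fails for clinic entrants who later start dialysis, if they are meant to be included. Followed literally, the definition reports time since a calendar date under the name of time since dialysis initiation. For an individual the discrepancy equals the whole of the earlier time on dialysis. Under the assumed mixes above, the mean would be 15 to 57 months from dialysis start where the entry-based figure is 12.

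The consequences are contained. The plan lists this outcome as exploratory, and nothing in the primary analysis, the fixed-sequence testing or the power calculation depends on it. The conclusion rests on the text available here. If the published protocol already limits the measure to patients entering at dialysis start, this table only needs to say so.

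**What to change.** 1. Limit the measure of dialysis initiation to referral to patients whose trial entry is their start of maintenance dialysis during the accrual period, so that the two dates coincide.
2. Report patients already on dialysis on November 1, 2017 separately, labelled as time from November 1, 2017 (trial entry) to referral. The plan already distinguishes these groups for its subgroup analyses.
3. State that patients who entered before dialysis from a multi-care kidney clinic are not in this measure. Do not select them on whether they were referred before dialysis: referral is a step the intervention aims to increase, so that selection could differ by arm.

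The cost is a short change to the definition, a re-cut of existing data, and fewer patients in an exploratory measure. If the change is made after the data were viewed, it must be labelled post hoc.
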